8.2.3 Figures

Figure 1. Flow Chart of Subjects Disposition

	Form	Form No.	1M-DMST-011-01-A1
	Statistical Analysis Plan	Page	Page 69 of 69
		Effective Date	07/05/2018

Figure 2. Flow Chart of Analysis Sets

RUN: DDMMYYYY HH:MM

<1MED > Page X of Y

Figure 3. Concentration by time plot (ITT Analysis Set)

Figure 4. Concentration by time plot by treatment group (ITT Analysis Set)

Figure 5. Concentration by time plot by gender (ITT Analysis Set)

Figure 6. Concentration by time plot for the single dose phase (ITT Analysis Set)

Figure 7. Concentration by time plot by gender for the single dose phase (ITT Analysis Set)

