6 INTRODUCTION

6.1 Background

Coenzyme Q10 (CoQ10) is a substance similar to a vitamin. It is found in every cell of the body. The body produces CoQ10, and the cells use it to produce energy for the body needs for cell growth and maintenance. It also functions as an antioxidant, which protects the body from damage caused by harmful molecules. CoQ10 is naturally present in small amounts in a wide variety of foods, but levels are particularly high in organ meats such as heart, liver, and kidney, as well as beef, soy oil, sardines, mackerel, and peanuts.

The Coenzyme Q10, also known as ubiquinone, is an endogenous molecule, synthesized by our body and essential for the proper functioning of the mitochondria, or the cellular units responsible for the production of energy in the body.

In organisms it participates in redox reactions and, depending on the state of oxidation, it can be present in three forms: an oxidized, a semi-quinone intermediate and a reduced form. The side chains make it very lipophilic, in fact it is present in biological membranes, especially mitochondrial ones.

Higher levels of Q10 could improve the efficiency of the electron transport chain, increasing the available energy.

Rebalancing the function of the mitochondria, which are in practice the "lungs" of every single cell, means allowing the cell to restore its original energy potential, and, in a certain sense, to "rejuvenate" allowing it to "breathe" and use the available energy correctly.

If coenzyme Q is reduced by acquiring an electron it forms a radical called ubisemichinone (QH.). For further reduction the compound becomes a ubiquinol (QH2).

The concentration of coenzyme Q10 tends to decrease with aging; low levels are also recorded in the presence of particular chronic diseases, such as those resulting from heart problems, Parkinson's disease, muscular dystrophy, diabetes, cancer and AIDS. Certain drugs, such as statins used in the control of hypercholesterolemia, can also lower Coenzyme Q10 levels.

Coenzyme Q10 has been shown to have beneficial effects on some patients with migraine and is a major component of the myth cocktail used in the treatment of mitochondrial myopathy and other metabolic disorders.

Taking 100 mg a day or more of CoQ10 has caused mild insomnia in some people. And research has detected elevated levels of liver enzymes in people taking doses of 300 mg per day for long periods of time. Liver toxicity has not been reported.

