Other reported side effects include rashes, nausea, upper abdominal pain, dizziness, sensitivity to light, irritability, headache, heartburn, and fatigue.

Medicines for high cholesterol (statins) and medicines that lower blood sugar cause a decrease of CoQ10 levels and reduce the effects of CoQ10 supplements. CoQ10 can reduce

	Study Title	Bioavailability Study of COQUN ORAL FORMULATION (CoQ10) administered in Healthy Adults (CoQ10-01)		
	Study ID	VF-BAQ10/2018	Sponsor:	VISUFARMA SpA
	Date	March 03, 2018	Vers.	Final

the body's response to the blood thinner (anticoagulant) medicine warfarin (Coumadin) and can decrease insulin requirements in people with diabetes.

Many factors can affect the Q10 blood level of people who are not taking a Q10 supplement: age, diet, disease, medications (for example, statin medications).

Q10 levels in the blood from the body's own synthesis of the substance increase after (0.20 ug/ml) birth until about the age of 21. Thereafter, the body's synthesis of Q10 gradually decreases.

It is expected that supplementing regularly with Q10 to raise the Q10 blood level, but much depends on the way in which the Q10 product has been prepared and much depends on the dosage. It was demonstrated that taking 30 milligrams or 50 milligrams of Q10 daily will not raise the Q10 level as much as taking 100 mg of Q10 daily will do, while taking 100 milligrams of Q10 twice daily will yield even greater gains in Q10 blood levels.

From the literature it is known that a well-absorbed Q10 supplement should over time raise the blood level to about 2.5 micrograms per milliliter if the individual is taking a 100-milligram dosage once a day, while if taken the same Q10 supplement in a dosage of 100 milligrams twice a day, its blood level should, over time, raise the steady-state Q10 blood level to somewhere in the area of 3.5 micrograms per milliliter. But, the attainable levels will vary from individual to individual, beside depending on the product itself as formulation.

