12.5 Subgroup Analysis

N.A

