3.2 Subgroups

No subgroup analysis has been planned in this study.

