	Statistical Analysis Plan	Page	Page 22 of 69
		Effective Date	07/05/2018

Analysis of Primary Efficacy variable:

Descriptive statistics such as mean \pm standard deviation, median with interquartile range, minimum, maximum and coefficient of variation will be presented for the plasma concentration of coenzyme Q10 at each time point in the entire sample of subjects. 95% confidence interval will be provided as well.

An explorative analysis on gender will be performed showing descriptive statistics for plasma concentration of coenzyme Q10 by gender. The effect of gender will be explored by means of a mixed model for repeated measures with covariates *gender*, time and the interaction term *gender*time*.

Descriptive statistics will be also provided for the plasma concentration of coenzyme Q10 at each time point by treatment group.

Change of plasma concentration versus baseline (i.e. change versus visit 2 values) will be computed for each study visit both for the whole sample and by treatment group.

Change will be computed in the following way:

$$\text{Change (\%)} = \frac{\text{Value at Visit X} - \text{Baseline Value}}{\text{Baseline Value}} \times 100$$

Area under the curve, maximum concentration in the plasma, time of maximum concentration and terminal half-life will be presented descriptively on the original scale.

95% confidence interval will be provided for the means of 100mg OD and 100mg BID for COQUN ORAL FORMULATION for the parameters AUC_t , C_{max} , T_{max} and terminal half-life. A Student t-test for unpaired data will be performed in order to detect differences between the two groups in the pharmacokinetics parameters.

A concentration by time graph will be presented for the multidose phase by treatment group in order to have a graphical visualization of the pharmacokinetics properties over time.

Line graphs will be provided for the concentration of coenzyme Q10 in the whole sample and by gender.

In performing statistical analysis, it is important to assess the statistical outliers. In fact, inclusion or exclusion of outlying subjects may lead to a different conclusion in assessment of differences in bioavailability between two formulations. It is therefore important to identify these outliers and study their effects.

Primary endpoint will be evaluated on the ITT population and analysis will be replied on the PP population. Results obtained on the PP population will be considered as supportive of those obtained on the ITT set.

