6. CHANGES TO THE ANALYSIS AS LAID DOWN IN THE PROTOCOL AND AMENDMENTS

No changes to the analysis as laid down in the protocol were made.

1MED Regulatory & Clinical Development	Form	Form No.	1M-DMST-011-01-A1
	Statistical Analysis Plan	Page	Page 31 of 69
		Effective Date	07/05/2018

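### The exploratory gender analyses of CoQ10 concentration adjust neither for age nor, in the multidose phase, for dose group, and SAP 3.2 and section 6 do not acknowledge them

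*SAP*

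**What the plan says.** SAP 5.2.1 (multidose phase) announces the work: "An explorative analysis on gender will be performed showing descriptive statistics for plasma concentration of coenzyme Q10 by gender". It adds a repeated-measures mixed model with gender, time and gender*time. SAP 5.2.3 plans the same for the single-dose phase. The outputs are Tables 14, 26 and 27, "Figure 5. Concentration by time plot by gender (ITT Analysis Set") and "Figure 7. Concentration by time plot by gender for the single dose phase (ITT Analysis Set"). The tables and figures are repeated on the per-protocol set.

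Three statements elsewhere do not fit this:

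- SAP 3.2: "No subgroup analysis has been planned in this study".
- SAP section 6: "No changes to the analysis as laid down in the protocol were made".
- The protocol section headed "12.5 Subgroup Analysis", whose whole content is N.A.

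On age, Protocol 6.1 says "The concentration of coenzyme Q10 tends to decrease with aging" and "Many factors can affect the Q10 blood level of people who are not taking a Q10 supplement: age, diet, disease, medications". Gender is not in that list. Protocol 8.2 admits subjects aged 35 to 75. SAP 5.1.2 collects age at Visit 1, but age then appears only in the demographics (Table 5, Listing 5) and in the demographic columns of the adverse event listings.

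**The concern.** Men and women are not randomised groups. If those enrolled differ in mean age, and CoQ10 falls with age, part of any gender difference will be an age difference that neither model can separate. The multidose model has a second problem. It pools subjects on 100 mg and 200 mg a day with no treatment term, so an uneven gender split across the arms would show up as a gender effect.

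At stake is how the gender curves and model terms are read in the study report. The documentation adds to this: a report following section 6 would present these outputs as part of the protocol's own analysis, which they are not.

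**Working it through.** The plan states no figure that could be reproduced here. The check sets the texts side by side and then shows how large the confounding could be.

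**1. Texts.** Protocol section 12 contains no gender analysis and no mixed model. Protocol 12.1 allows additional analyses provided the SAP explains them. SAP 5.2.1 and 5.2.3 describe the gender work but give no reason for choosing gender, and section 6 reports nothing added. Both models list gender, time and gender*time only.

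**2. Age.** From the documents: ages 35 to 75 (Protocol 8.2) and 24 subjects (Protocol 12.3). Assumed: ages spread evenly over the range, 12 men and 12 women, no true gender difference, and an age-CoQ10 correlation r of -0.3 to -0.5.

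- SD of age = 40/√12 = 11.55 years.
- SE of the difference in mean age = 11.55 × √(1/12 + 1/12) = 4.71 years; 95% range ±1.96 × 4.71 = ±9.2 years.
- Median absolute chance gap = 0.6745 × 4.71 = 3.2 years.
- Spurious gender difference in SD units = |r| × gap/11.55:

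| Age gap | \|r\| = 0.3 | \|r\| = 0.4 | \|r\| = 0.5 |
|---|---|---|---|
| 3.2 years | 0.08 | 0.11 | 0.14 |
| 5 years | 0.13 | 0.17 | 0.22 |
| 10 years | 0.26 | 0.35 | 0.43 |

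- Chance alone gives a gap of 5 years or more with probability P(\|Z\| ≥ 5/4.71) = 29%, and of 10 years or more with P(\|Z\| ≥ 10/4.71) = 3.4%.
- For scale, the SE of the gender difference itself at one time point is √(1/12 + 1/12) = 0.41 SD.
- Rejection rate of an unadjusted two-sided 5% t-test (noncentral t, 22 df) with the gap held fixed: 5.4% to 6.2% at 3.2 years; 9.3%, 12.8% and 17.4% at 10 years for the three correlations. Averaged over chance gaps, simulation gives 4.9% to 5.0%.

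These are single-time-point calculations. The repeated-measures model would differ according to a within-subject correlation that the documents do not give.

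**3. Dose group.** Protocol 6.1 expects about 2.5 µg/ml on OD and 3.5 µg/ml on BID over time, a difference of 1.0. The spurious difference (women minus men) is then 1.0 × (proportion of women on BID − proportion of men on BID). Assuming 12 women and 12 men:

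- 7 women and 5 men on BID: 7/12 − 5/12 = 0.17 µg/ml.
- 8 women and 4 men on BID: 8/12 − 4/12 = 0.33 µg/ml.

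Protocol 9.6 and SAP 2.3 mention no stratification. If 24 subjects are randomised 12:12 without regard to gender, the chance of an 8:4 split or worse in either direction is 1 − [C(12,6)² + 2 × C(12,5)²]/C(24,12) = 1 − (853,776 + 1,254,528)/2,704,156 = 22%. The single-dose model does not have this problem, since all subjects take 100 mg.

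**The case against.** **The gender analysis is permitted and already labelled.** A reader might infer that the protocol ruled out a gender analysis. It did not. Section 12.5 says only N.A., 12.1 provides for additions explained in the SAP, and 12.6 describes the aim as exploring and describing data. Both SAP sections call the work explorative. This objection stands. What remains is that section 6 does not list the addition and that 3.2 reads against it.

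**SAP 3.2 may be true in a narrow sense.** If a subgroup analysis means a treatment effect within subgroups, none is planned: the gender outputs have no treatment columns, and AUC, Cmax, Tmax and half-life are not split by gender. This is a fair reading, so the mismatch with 3.2 is partly terminology. The mismatch with section 6 is not.

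**The error rate is not generally inflated.** A reader might infer from the 9% to 17% rejection rates that the unadjusted gender test is broadly invalid. Those rates hold only at a fixed 10-year gap, which chance alone gives about 3% of the time under the assumptions above. Averaged over chance gaps the test keeps about its 5% level. Inflation needs a systematic age difference between the men and women recruited, and the documents give no evidence of one.

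**Age adjustment was never promised.** This is correct. The protocol's list of factors also concerns people not taking a supplement, so it bears on the gender main effect more than on gender*time. The omission is a weakness in the model's rationale, not a departure from a stated plan.

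**Conclusion.** The point holds as a modest one. The SAP adds permitted exploratory gender analyses of CoQ10 concentration that are non-randomised and unadjusted for age, and in the multidose phase it pools the two dose groups. An age gap between men and women, or an uneven gender split across arms, would be read as a gender effect.

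The size cannot be known in advance. A typical chance age gap gives about 0.1 SD, small against a standard error of about 0.4 SD; a systematic 10-year gap would give 0.26 to 0.43 SD. These rest on assumed even ages, a 12:12 gender split and a correlation of 0.3 to 0.5 in absolute value. The dose-group figures rest on the same assumed split and on the protocol's literature values.

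The inconsistency with section 6 needs no assumptions, but correcting it changes no result. It would also be wrong to infer that the dose conclusion is at risk: the OD versus BID comparison does not depend on gender.

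**What to change.** 1. Add Visit 1 age (continuous) as a covariate to the gender mixed models in SAP 5.2.1 and 5.2.3.
2. Add treatment group to the multidose model in 5.2.1. Visit 2 precedes multidose intake, so a treatment-by-time term could be considered as well if gender*time is to be interpreted.
3. Report n and mean age per gender with Tables 14, 26 and 27 and Figures 5 and 7. The plots cannot be age-adjusted, so this is what lets a reader judge them.
4. As housekeeping, reword SAP 3.2 to say that gender is explored as an addition to the protocol, and list the gender analyses in section 6 as exploratory additions with the reason for them.

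The cost is one degree of freedom in the single-dose model and two in the multidose model (three more, for four visits, if treatment-by-time is included), plus SAP wording before the database is locked. No new data are needed, since age, gender and treatment group are already collected.
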